## **6.2 Study population**

### *6.2.1 Inclusion criteria*

- Women  $\geq$  18 years of age.
- Women with clinical manifestations of infectious VV.
- Women who agree to participate by signing the informed consent form.

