### *6.2.2 Exclusion criteria*

- Symptoms (high suspicion) compatible with infection due to *Chlamydia trachomatis*, *Trichomona vaginalis*, *Neisseria gonorrhoeae* or *Herpes simplex*.
- Use of antifungal or probiotic agents during the last 2 weeks prior to the study.
- Patients who are receiving any other treatment with probiotics, vitamin complexes that may significantly interfere with the study assessments.
- Pregnant patients.
- Patients who may become pregnant (if there is a reasonable doubt about the possibility of pregnancy at the time of inclusion or during the study a blood pregnancy test will be performed to rule out this possibility).
- Patients who are menstruating at the time of inclusion.
- Breast-feeding patients.
- Immunocompromised patients.
- Patients who, based on the investigator's criteria, are not expected to complete the follow-up.

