### *6.2.3 Rescue criteria*

In cases where the patient requires "rescue treatment", the treatments will be crossed. In the event of changing treatment group (crossover), the patient will be considered to be back at V0 and the tests/examinations corresponding to the baseline visit will be repeated.

The patient will change group to receive alternative treatment in the following cases:

- Patient with hypersensitivity to the first assigned treatment.
- Worsening of symptoms within 3-4 days of starting the assigned treatment.
- Evidence or indications of lack of effectiveness after the first assigned treatment.
- Patient who demonstrates a willingness to change treatment.
- In cases where the perceived lack of effectiveness is associated with a suspected mixed aetiology infection (candidal and bacterial):
  - If they are in the control group, they will be changed to the treatment under study (boric acid + *L. gasseri* and *L. rhamnosus*).
  - If they are in the study group, they will be changed to the antifungal treatment (Gine-Canesten®; Clotrimazole 100 mg). If this treatment fails, BV will be treated with antibiotic treatment (Dalacin®; Clindamycin 100 mg).

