### 6.3.3 Baseline Visit – $V_0$ (inclusion)

After the case history and initial examination, which will serve to substantiate the suspicion of VV due to infection, patients will be recommended to participate in the trial provided they meet the inclusion/exclusion criteria. Once the patient Information Sheet (PIS) has been handed over, the patient has signed the Informed Consent (IC) form and the investigator has verified that the patient meets the inclusion and exclusion criteria, they will proceed to fill in the CRF baseline visit sections.

During this first visit, socio-demographic data, relevant clinical history and gynaecological history will be recorded. The investigator will assess the patient's symptoms by recording the presence of clinical signs and symptoms of infectious VV (stinging, itching, erythema, oedema, abnormal vaginal discharge, etc.) and the *Sobel score* (see section 7.0). The vaginal pH determination test will then be carried out and the samples for the different laboratory tests will be collected, which will consist of: spreading the vaginal discharge sample on a slide to subsequently count the *Lactobacillus spp.* and collecting the discharge sample with a swab that will also be used for the diagnostic confirmation culture and for the fresh vaginal smear. The samples will be stored properly according to the instructions specified in the manual of use of the sampling kit until the samples are collected.

The patient will be given the treatment corresponding to the code assigned to her, reminding her that she has the possibility of changing treatment group, at the time that she deems appropriate. If the assigned treatment is ineffective or

is not tolerable, the patient may contact the hospital to bring the first control visit forward and request a change of treatment.

During the baseline visit, the patient will be given a CRF which she must fill in and return at the end of the visit and a card with a link to the online home CRF (Patient diary) that must be filled in over the course of the study. The home CRF will be used to monitor the patient during the follow-up weeks. The home CRF may also be delivered on paper and the patient must deliver it later.

The investigator will give the patient product for one treatment cycle (which may range from 3 days (Clindamycin) to 7 days (boric acid 150 mg, *L. gasseri*, *L. rhamnosus*)).

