### **11.5 Follow-up of patients with AE**

Patients can be withdrawn from the CT at any time. Patients who have been withdrawn from the study due to an AE must be monitored by the investigator until the clinical result of the AE is determined.

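### No eligibility criterion excludes women with known hypersensitivity to a trial product, and the rescue rules choose the next product without an allergy condition

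*Combined protocol and SAP*

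**What the plan says.** Section 6.2.1 has three inclusion criteria: age, consent, and a clinical presentation worded as "Women with clinical manifestations of infectious VV". Section 6.2.2 has nine exclusions. None names allergy, hypersensitivity or a contraindication to any trial product. The only exclusion left to the investigator's judgement concerns patients who "are not expected to complete the follow-up".

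Hypersensitivity appears in section 6.2.3, first in the list of reasons for moving to the alternative treatment: "Patient with hypersensitivity to the first assigned treatment". On such a move the plan states: "In the event of changing treatment group (crossover), the patient will be considered to be back at" V0, and the baseline tests are repeated.

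The same section fixes the rescue product when a mixed infection is suspected. For the control arm: "If they are in the control group, they will be changed to the treatment under study". A study-arm patient goes to clotrimazole, and then: "If this treatment fails, BV will be treated with antibiotic treatment". Section 6.3.5 lets the investigator suggest the other therapeutic option according to aetiology. Section 9.2 allows rescue with the study's alternative and bases the suitability of treatment on the diagnosis.

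Section 6.3.3 takes a history before enrolment ("After the case history and initial examination, which will serve to substantiate the suspicion of VV due to infection"), records relevant clinical history and verifies the listed criteria. Section 11.5 adds a general exit: "Patients can be withdrawn from the CT at any time".

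**The concern.** Crossover is part of this design and easy to trigger. Worsening, lack of effectiveness or the patient's own wish is enough under 6.2.3, so any participant may meet a second product, and some may meet all three. Whether a woman can safely receive each of them is therefore an eligibility question, and it can be asked before the code is assigned.

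Two things are at stake. The main one is safety: the written rescue path can lead to a product to which a woman is known to be allergic. The other is an avoidable, non-random change of group or withdrawal when the allergen is the product assigned first. Section 8.2 does not say how a patient who changes group is analysed, so her outcome could be kept or lost.

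**Working it through.** The point is mainly textual, and the plan gives no figure of its own to reproduce.

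**Step 1: would the written eligibility check stop her?** No. Section 6.3.3 verifies the criteria in 6.2.1 and 6.2.2, and 0 of 3 and 0 of 9 concern allergy. The history may reveal an allergy, but no criterion acts on it.

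**Step 2: where can the allergen be met?**

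- *Allergic to the study product.* Assigned to study: she receives the allergen, and 6.2.3 gives a change of group or 11.5 a withdrawal. Assigned to control: rescue leads to the allergen.
- *Allergic to the control drug for her aetiology.* Assigned to control: change of group or withdrawal. Assigned to study: rescue leads to the allergen.
- *Allergic only to the other control drug.* She meets it only in the study arm, through the mixed-infection sequence of clotrimazole and then clindamycin.

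Under the 1:1 ratio (6.1, 6.5), a woman in either of the first two rows has a 1/2 chance of being assigned the allergen and a 1/2 chance of having it as her rescue product. The second 1/2 is not a chance of exposure. Exposure also needs a rescue to occur and the allergy to be overlooked.

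**Step 3: does the return to V0 catch it?** Not as written. Tests and examinations are repeated, but re-checking the listed criteria would not help, because allergy is not among them. The 6.2.3 item covers only the treatment assigned first, and the discontinuation criteria (6.2.4) do not list hypersensitivity to the rescue product.

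**Step 4: statistical size per affected patient.** Inputs: minimum of 50 patients (6.8) and 1:1 allocation.

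- Patients per arm: 50/2 = 25, so one patient is 1/25 = 4% of an arm.
- If she is dropped, the standard error of the difference is multiplied by √(1/24 + 1/25) / √(2/25) = 1.0104, a rise of 1.0%. This takes equal variances in the two arms.
- If she is kept as assigned but has the other arm's expected outcome, the contrast is multiplied by 1 − 1/25 = 0.96, a loss of 4%.

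**Step 5: how many patients (assumption only).** The documents give no allergy frequency. Let p be the proportion of candidates allergic to the study product or to their own control drug. The expected number assigned the allergen first is 50 × p/2: 0.125 at p = 0.5%, 0.25 at 1%, 0.5 at 2% and 1.25 at 5%. This takes every allergic candidate to be enrolled, so it is an upper figure for each p.

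**The case against.** The strongest reply is that a known allergy would have to be missed by both the clinician and the patient. A case history precedes enrolment, relevant clinical history is recorded, the trial is open with ordinary market labelling (10.2), gynaecologists give the treatment, and GCP applies (9.1). Rescue is also partly discretionary: 6.3.5 and 9.2 say that it may happen, although 6.2.3 is firmer. All of this stands as a reason to expect few exposures. None of it is a written rule that acts on a known allergy.

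Four stronger readings are tempting and are not supported.

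- *The 6.2.3 item shows that the plan means to enrol allergic women and switch them.* The item sits beside worsening within days of starting and lack of effectiveness, so it most naturally means a reaction arising on treatment. Nor does 6.2.3 say anything about switching before the first dose. On this reading, pre-existing allergy simply has no rule.
- *There is a substantial chance of harm.* The Step 5 assumption gives a chance of at least one first assignment to an allergen of 1 − (1 − p/2)^50, which is 12% at p = 0.5% and 72% at 5%. That range rests wholly on the assumed p, ignores women declined after the history, and measures first assignment rather than the rescue exposure where the safety concern lies. It should carry no weight.
- *The treatment comparison is materially distorted.* Step 4 shows a small effect per patient, and there may be no such patient.
- *No safeguard exists anywhere.* The CRF and the consent annexes were not available and may ask or warn about allergy. Even so, a question or warning there would not be an eligibility criterion.

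**Conclusion.** The point holds as an omission in the eligibility and rescue rules of the protocol text. Followed to the letter, they admit a woman with a known allergy to a trial product and can direct her to that product, either at assignment or at rescue. This conclusion rests on the text alone and does not depend on any allergy frequency.

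Actual exposure is probably rare, and its frequency cannot be estimated from the documents. The statistical consequence is small: a 1.0% larger standard error, or a 4% smaller contrast, for one affected patient among 25. The case for change is patient safety and the removal of an avoidable crossover. It is an improvement that could be made, at low cost, and not a flaw that undermines the trial.

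**What to change.** Add to 6.2.2: *known hypersensitivity to boric acid, the lactobacilli, the prebiotics, clotrimazole, clindamycin or any excipient*, to be checked before the code is assigned. In 6.2.3, limit the hypersensitivity item to reactions that first appear after assignment. Because the exclusion covers every product a patient may meet, it also closes the rescue path for known allergies.

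The cost is one line in 6.2.2, a few words in 6.2.3 and an allergy check at V0, which the CRF may already contain. Some otherwise eligible women are lost. Under the assumed p of 0.5% to 5%, reaching 50 patients needs 50/(1 − p) − 50 = 0.25 to 2.63 extra candidates. The full wording costs somewhat more, since it also removes women allergic only to a drug they would meet at rescue, such as a candidal patient allergic to clindamycin.

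A narrower option is to exclude only for the study product and the control drug for the suspected aetiology, and to check the third drug before rescue. The suspected aetiology would then have to be recorded before the code is assigned, whereas 6.4 indicates the control drug after randomisation.

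Neither option removes the other crossover triggers in 6.2.3 or settles how 8.2 should treat patients who change group.

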#### 6.2.4 Discontinuation criteria

- Patients who, during the study period, receive/use some type of treatment and/or intervention (probiotics, vitamin complexes or vaginal showers) that may significantly interfere with the study assessments.
- Patients who, even while receiving the rescue treatment, show a lack of effectiveness\*. Patients who, after the baseline visit, are suspected to have an infection due to *Chlamydia trachomatis*, *Trichomona vaginalis*, *Neisseria gonorrhoeae* or *Herpes simplex*.

\*These patients will also be subject to follow-ups during the 3 months of study.

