### 7.3 End points

- Number of patients with VV recurrence during the follow-up period in each treatment group (incidence of recurrences after 3 months).
- Number of patients with resolved symptoms in each group 2 weeks after finishing the treatment.
- Changes in vaginal pH level in each group.
- Number of patients with “*clue cells*” or hyphas in the fresh smear.

- Profile and proportion of pathogen isolation in culture.
- Increase in the population of *Lactobacillus spp.* post-treatment.
- Rescue success rate in different scenarios.
- Relationship between compliance and treatment effectiveness.
- Relationship between compliance and recurrence after 3 months.
- Percentage of cases with good treatment tolerability.
- Rate of adverse events.
- Treatment tolerability.
- Proportion of patients with mixed infections (VC + BV).

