### **8.2 Objectives of the study**

The analysis of the main objective will focus on the comparison of the effectiveness of the product under study (boric acid + *L. gasseri* and *L. rhamnosus*) and that of the control treatment with solid vaginal forms, according to the usual clinical practice (clotrimazole or clindamycin) and assessed according to the patient's clinical symptom scores (VAS, Sobel score) approximately 2 weeks after the end of the treatment. To do this, T tests for independent samples or non-parametric Mann–Whitney U tests will be used.

For the secondary objectives, the level of restoration of vaginal flora will be assessed by comparing the *Lactobacillus* count in baseline discharges and 2 weeks after treatment through T tests for related samples or non-parametric

Wilcoxon or McNemar tests. The incidence of recurrences/relapses at 3 months will be studied by means of proportion comparison tests (Pearson's chi-squared test). The characterisation of the different symptomatic and microbiological profiles of VV, as well as the tolerability, compliance and adverse events, will be analysed through descriptive statistics.

The possibility of carrying out additional analyses, depending on the results, with the relevant statistical tests in each case is not ruled out.

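### Vaginal showers are named as interfering during the study (6.2.4) but not at entry (6.2.2), so baseline pH and Lactobacillus can be measured under an exposure the protocol restricts only afterwards

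*Combined protocol and SAP*

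**What the plan says.** **On study.** Section 6.2.4 applies to "Patients who, during the study period, receive/use some type of treatment and/or intervention" and lists in parentheses "probiotics, vitamin complexes or vaginal showers) that may significantly interfere with the study assessments".

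**At entry.** Section 6.2.2 has two relevant exclusions. One concerns current use: "Patients who are receiving any other treatment with probiotics, vitamin complexes that may significantly interfere with the study assessments". The other is a look-back: "Use of antifungal or probiotic agents during the last 2 weeks prior to the study". Neither mentions vaginal showers.

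**Measurements.** Section 6.3.3 places the measurements at baseline: "The vaginal pH determination test will then be carried out and the samples for the different laboratory tests will be collected". These include "spreading the vaginal discharge sample on a slide to subsequently count the" Lactobacillus population. Section 6.3.5 repeats the tests and samples at V1, about two weeks after treatment ends.

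**Use of the measurements.** Section 8.2 states that "the level of restoration of vaginal flora will be assessed by comparing the" Lactobacillus count at baseline with the count two weeks after treatment, by a paired t test, Wilcoxon or McNemar test. It names no between-arm test for this objective. Section 7.3 lists "Changes in vaginal pH level in each group" as an end point, and no test is specified for it.

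**The concern.** V0 is itself a study assessment. If showers can disturb pH and flora readings after V0, they can disturb them at V0 too. The entry criteria leave that side open, while 6.2.4 closes the other.

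Two consequences follow.

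- **A woman who used showers up to V0 and then stops.** Her V0 reading reflects the exposure and her V1 reading does not. Any change caused by stopping enters the before-after difference and is read as restoration by treatment. Randomisation does not protect a change computed within one arm.
- **A woman who continues.** She may meet a 6.2.4 criterion for a habit that one question before randomisation would have identified. With a stated minimum of only 50 patients, even a few such cases matter.

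At stake is a named secondary objective, flora restoration, together with the pH end point.

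**Working it through.** **Step 1. Compare the lists.**

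| Item | Look-back at entry (6.2.2, two weeks) | Current use at entry (6.2.2) | During study (6.2.4) |
|---|---|---|---|
| Antifungals | named | not named | not named |
| Probiotics | named | named | named |
| Vitamin complexes | not named | named | named |
| Vaginal showers | not named | not named | named |

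Showers are the only item named on study and nowhere at entry.

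**Step 2. Look for another passage that closes the gap.**

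- Section 6.3.3 records clinical and gynaecological history at V0 but names no question on showers. The case report form is not among the documents.
- Section 6.6 records concomitant treatments. It does not mention showers or use before V0, and section 8 makes no use of the record.
- The first scripted check on interfering products is the telephone interview at about 8 weeks (6.3.6). That is after V1, which 6.3.4 puts at about 21 days from V0.

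Nothing found closes it.

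**Step 3. Trace it to the analyses.**

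- Lactobacillus: V1 against V0 within arm. Exposed.
- pH: change within group. Exposed.
- Main objective: symptom scores compared between randomised arms about two weeks after treatment. V0 pH and Lactobacillus values do not enter, and prior shower use is balanced between arms in expectation. Not biased by this route, although chance imbalance is possible at this sample size.

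**Step 4. Illustrate the size.** The plan gives no figure to reproduce: no share of users, no effect of stopping, no SD and no scale for the count. Everything below except the arm size is assumed.

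- Arm size: 50 / 2 = 25 (minimum of 50 in 6.8, ratio 1:1 in 6.1).
- p = share of an arm that used showers up to V0 and then stopped.
- s = shift in the change score from stopping, in SDs of the change.
- Bias in mean within-arm change = p × s.
- Women affected per arm = 25 × p: 2.5 at 10%, 5 at 20%, 10 at 40%.

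Rejection rates come from 20,000 simulated trials per row. There was no treatment effect, change scores were normal with SD 1, p was the same in both arms, and t tests were two-sided at 5%.

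| p | s | Bias p × s (SD) | Within-arm paired test rejects | Between-arm test on change rejects |
|---|---|---|---|---|
| 10% | 0.5 | 0.05 | 5.6% | 4.7% |
| 10% | 1.0 | 0.10 | 7.3% | 5.2% |
| 20% | 0.5 | 0.10 | 7.8% | 5.2% |
| 20% | 1.0 | 0.20 | 14.3% | 5.0% |
| 40% | 0.5 | 0.20 | 15.9% | 5.2% |
| 40% | 1.0 | 0.40 | 40.2% | 4.8% |

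With p = 0, both tests reject at about 5%. The within-arm test loses its nominal level as p × s grows; the between-arm test does not. The 40% rows show the trend and are not a likely value.

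**The case against.** The other side has several fair points.

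- **Omission is not permission.** A reader might infer that the protocol allows showers up to V0. It says nothing about them there. Hence baseline readings can be affected; the documents do not show that they are.
- **Stopping is not documented.** A reader might also infer that the exposure is removed before V1. That is implied by 6.2.4, but no section tells women to stop at V0 and nothing scripted checks it before the 8-week call.
- **Continuing is not clearly loss to the trial.** The wording of 6.2.4 leaves room for judgement on whether interference is significant. Section 6.6, citing 6.2.4, speaks of withdrawing the product, and treatment lasts only 3 to 7 days. The footnote to 6.2.4 assures follow-up only for the patients it marks, so loss of data is possible but not stated. The investigator may also exclude at entry a woman not expected to complete follow-up.
- **Entry and on-study lists need not be identical.** They differ in the other direction too: antifungals are in the look-back but not named in 6.2.4.
- **A before-after test in symptomatic women is weak anyway.** Natural resolution and regression to the mean also enter it. The more basic gap is the absence of a between-arm comparison for Lactobacillus.

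The first three points limit what can be claimed, and they stand. The fourth explains that lists may differ, but not why something judged to interfere after V0 should be ignored at V0. The discretionary exclusion does not reach a woman who simply stops. The fifth stands and shapes the fix.

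**Conclusion.** The mismatch between 6.2.2 and 6.2.4 is real, and no other passage closes it. Baseline pH and Lactobacillus can be measured under an exposure that the protocol treats as interfering from then on. In women who used showers up to V0 and then stopped, the two within-arm change results can attribute the effect of stopping to treatment.

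It would be wrong to conclude that the trial's main result is biased. That result is a randomised between-group comparison of symptom scores, which this does not bias in expectation.

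The size is unknown. The 0.05–0.20 SD bias and the 6–14% rejection rate hold only if 10–20% of an arm used showers and stopped, and if stopping shifts the change by 0.5–1.0 SD in the direction of apparent restoration. The documents support none of these values; even the direction is assumed. The between-arm rate near 5% assumes that stopping is equally common in both arms, which an open trial does not guarantee.

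This is an inexpensive improvement to secondary results in a pilot. It is worth making before recruitment.

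**What to change.** 1. Reconcile the lists in 6.2.2 and 6.2.4, so that recent vaginal shower use is covered at entry as it is on study. The existing two-week look-back is a natural place for it. State also what 6.2.4 means for data collection once the short treatment course is over.
2. Ask for and record the date of last use in the V0 history, before the code is assigned.
3. If such women are still enrolled, compare Lactobacillus and pH change between arms, adjusted for the V0 value. Add a sensitivity analysis without women who report recent use at V0. This restriction depends on pre-randomisation status only. Do not drop them from the main change analysis: on the assumed 10–20%, that would discard 2.5–5 of 25 pairs per arm and would do nothing about women who continue.

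**Cost.** One history question and a small loss of candidates if use becomes an entry criterion. The between-arm comparison asks a harder question of a small trial. With 25 per arm and no gain from baseline adjustment, the difference detectable with 80% power at two-sided 5% is (1.96 + 0.84) × √(2/25) = 0.79 SD. The result should therefore be reported as an estimate with a confidence interval.

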### 6.3.2 Follow-up period

Follow-up will be 3 months from the inclusion visit ( $V_0$ ). Patients should attend two control visits in person and answer two telephone interviews.

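### Three-month follow-up after discontinuation is provided only for patients who fail rescue; for the other two discontinuation groups none is provided, and no analysis set or missing-data rule fills the gap

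*Combined protocol and SAP*

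**What the plan says.** Section 6.2.4 names three groups to be discontinued:

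1. Users of a treatment or intervention of a listed kind: "probiotics, vitamin complexes or vaginal showers) that may significantly interfere with the study assessments".
2. Rescue failures: "Patients who, even while receiving the rescue treatment, show a lack of effectiveness".
3. Suspected chlamydia, trichomonas, gonorrhoea or herpes: "Patients who, after the baseline visit, are suspected to have an infection due to" one of these organisms.

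An asterisk directly follows the second criterion and leads to the footnote "These patients will also be subject to follow-ups during the 3 months of study". The first and third criteria carry no asterisk.

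Four other places bear on the point:

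- Section 6.3.2 sets the general period: "Follow-up will be 3 months from the inclusion visit". It does not say whether this continues after discontinuation.
- Section 6.6 refers to 6.2.4 and says that treatments able to influence the results lead to withdrawal of the product. It does not mention visits.
- Section 11.5 follows patients withdrawn for an adverse event until the outcome of that event is known. It states no efficacy follow-up.
- Section 8.2 gives the tests for symptom scores, *Lactobacillus* counts and recurrence. It names no analysis set and no rule for missing or discontinued patients.

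**The concern.** A footnote that keeps one discontinued group in follow-up suggests that the others are not kept. A patient who attends no further visit has no symptom score for the t test or Mann–Whitney test and no recurrence status for the chi-squared test.

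Losses of this kind occur after randomisation. If they are related to outcome or to arm, the patients who remain no longer represent those randomised. Three features of the design make such a relation plausible:

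- The trial is open (6.1, 10.2), and probiotics are both a component of the study product and a reason to discontinue. Control patients know that they are not receiving probiotics, so probiotic use could differ by arm.
- The 8-week call (6.3.6) looks mainly for recurrence and also asks about interfering products, with a reference to 6.2.4. A woman whose symptoms return and who treats herself could be discontinued at that call, before V2.
- Suspicion of another infection is a judgement by an investigator who knows the arm, and persistent symptoms can prompt it.

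These are inferences from the design. The documents do not state that the exits depend on response.

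**Working it through.** **Which groups have a follow-up rule**

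| Group | Follow-up stated after the event |
|---|---|
| First treatment fails (6.2.3) | Crosses over and restarts as at baseline |
| Rescue fails (6.2.4) | Yes, during the 3 months |
| Interfering product (6.2.4, 6.6) | None stated |
| Another infection suspected after baseline (6.2.4) | None stated |
| Withdrawn for an adverse event (11.5) | Until the event's outcome is known |

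**Which outcome is exposed**

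Section 6.3.4 places V1 at 21 days from V0. Section 6.3.6 places the call that checks for interfering products at about 8 weeks (56 days), and 6.3.7 places V2 at 3 months. A patient discontinued at the 8-week call would normally already have V1 data, so only her 3-month recurrence status is at risk. A patient discontinued before day 21 could lose both.

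**Size, by illustration**

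The plan has no figure to reproduce. Section 6.8 gives a minimum of 50 patients without a calculation, and no discontinuation rate appears anywhere.

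- From the documents: at least 50 patients (6.8) at 1:1 (6.1), so 50/2 = 25 per arm.
- Assumed: true resolution of 15/25 = 60% in both arms; *m* unfollowed patients, all failures and all in one arm.
- Observed rate in that arm = 15/(25 − *m*). Bias = observed rate − 60%, which is also the bias in the difference between arms.

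| *m* | Observed rate | Bias (points) |
|---|---|---|
| 1 | 15/24 = 62.5% | 2.5 |
| 3 | 15/22 = 68.2% | 8.2 |
| 5 | 15/20 = 75.0% | 15.0 |

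The same arithmetic serves for recurrence. If 10/25 = 40% truly recur and *m* of those are unfollowed, the observed rate is (10 − *m*)/(25 − *m*): 9/24 = 37.5%, 7/22 = 31.8% or 5/20 = 25.0%. The bias has the same size and makes the arm look better.

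Without assuming that the leavers are failures, *m* unknown outcomes leave the arm's rate uncertain over a range of *m*/25: 4, 12 or 20 points.

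**The case against.** The strongest reply is that the plan is silent and does not exclude anyone. Section 6.3.2 sets 3 months of follow-up with no exception for discontinuation, 6.6 withdraws the product rather than the patient, and the word *also* in the footnote could be a clarification. In the text as read, the third criterion runs on from the second, so the layout is weak evidence. This stands in part: a reader might infer that these patients are removed from the outcome data, and no section says so. The gap remains, because the footnote would be unnecessary if everyone were followed and no other section supplies the rule.

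A reader might also infer that the unfollowed patients are often non-responders. The documents do not support that. Non-response to the first treatment is a trigger for crossover ("Evidence or indications of lack of effectiveness after the first assigned treatment"), after which "In the event of changing treatment group (crossover), the patient will be considered to be back at V"0. Failure on rescue is the one group expressly followed. A symptomatic patient may also ask to change treatment at any time (6.3.3), which reduces the incentive to treat herself. Vitamin use or douching need not reflect persistent symptoms, and a suspicion of another infection could arise from the baseline results, which are recorded at V1 (6.3.5). Some link to response is possible; neither its existence nor its frequency is documented.

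The illustration is an adverse case: every leaver is a failure and all are in one arm. It also uses proportions, whereas the main analysis in 8.2 compares symptom scores. Both criticisms are fair, so the figures show sensitivity and are not a forecast.

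**Conclusion.** The point holds in a limited form. Follow-up to 3 months after discontinuation is provided only for rescue failures. It is not provided for users of interfering products or for patients with another suspected infection, and 8.2 has no analysis set or missing-data rule to cover the gap. The comparison chiefly exposed is 3-month recurrence; the V1 outcome is exposed only for patients who leave before V1.

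On the stated assumptions (25 per arm, 60% resolved, 1 to 5 failures unfollowed in one arm) the bias is 2.5 to 15 points. It would be smaller if leavers included successes or were spread across arms, and could be near zero if exits are rare or unrelated to outcome. The documents do not allow a choice within that range. The change is worth making because a few patients matter at this sample size and the remedy is simple.

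**What to change.** - **Section 6.2.4:** apply the follow-up footnote to all discontinued patients, so that every randomised patient who still consents is asked to attend the scheduled V1 and V2 whatever the reason for discontinuation. This would include the adverse-event withdrawals in 11.5.
- **Section 8.2:** analyse all randomised patients in the assigned arm, using outcomes collected after discontinuation. Add a sensitivity analysis that counts a missing outcome as a failure (not resolved at V1; recurrence at 3 months), and report the number missing by arm and reason.
- **No removal by baseline sample:** do not add a rule that removes patients according to the V0 sample result. Sections 6.3.3 and 7.1 name no specific test for the organisms concerned.

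The discontinuation rules stay as they are. How outcomes are dated after the crossover reset in 6.2.3 is a separate question that this change does not settle.

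The cost is a short amendment to two sections and a few visits that 6.3.2 already schedules. Whether they are funded cannot be checked, since 9.8 places the budget in a separate document. Retaining patients who used other products will dilute the treatment contrast somewhat. Counting missing outcomes as failures can itself mislead if losses differ by arm, so it belongs in a sensitivity analysis.
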